Eligible placebo non-responders will be randomized to one of two treatment sequences within their respective body weight stratum determined immediately prior to randomization: ZNS followed by placebo or placebo followed by ZNS ([Table 1](#)). Subjects weighing less than 50 kg will be allocated randomly to receive ZNS 2.5 mg or 1 mg in a 5:1 fashion during the ZNS treatment. Subjects weighing at least 50 kg will be allocated randomly to receive ZNS 5 mg or 2.5 mg in a 5:1 fashion during the ZNS treatment ([Table 2](#)). Following randomization, subjects will have up to 6 weeks to treat a migraine attack of moderate or severe intensity. During each treatment period, subjects will treat a single moderate to severe migraine attack with study drug within approximately 20 minutes of the headache pain reaching moderate or severe intensity. Headaches occurring while the child is at school will not be treated with study drug. Headache pain intensity will be assessed by the subjects immediately prior to treatment with study drug and at 30 minutes, 1, 2, and 24 hours postdose using a subject diary containing the 4-point headache pain intensity scale. Associated migraine symptoms will also be assessed at these time points. Subjects who do not obtain satisfactory relief of migraine pain by 2 hours after taking study drug will be permitted to treat with their protocol-allowed pre-study acute migraine medication (eg,

nonsteroidal anti-inflammatory drugs [NSAIDs] or acetaminophen) at that time or at any time thereafter, if the headache does not resolve or if it recurs, with the exception that all triptans and ergot derivatives are prohibited for 24 hours following the dose of study treatment. After treating a migraine attack in the first treatment period, the subject will return to the study site to receive study drug for the second treatment period. Subjects will then have up to 6 weeks to treat a second migraine attack of moderate or severe intensity.

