### **2.5.1.1. Imputation Method for Migraine Headache Diary Data**

1. If the predose diary is missing the pain intensity for a particular treatment period, then the subject is considered a non-responder for diary time points 0.5-hour, 1-hour, and 2-hour for that treatment period.
2. If all postdose pain intensity up to and including the 2-hour diary are missing for a particular treatment period, then the subject is considered a non-responder for those time points (0.5-hour, 1-hour, and 2-hour) for that treatment period.
3. If a subject receives rescue medication within 2 hours after dosing with study drug for a particular treatment period, the subject will be considered a non-responder for all the subsequent diary time points after rescue for that treatment period up to and including the 2-hour time point. Note: if subject diary includes records of rescue medication that started prior to the start of migraine, such medications will be ignored as incorrect diary entry. If rescue medications are recorded with missing start date/time, worse case will be assumed, i.e. that the rescue medication was taken at the same time as the migraine started.
4. If a subject naps or sleeps within 2 hours after dosing with study drug for a particular treatment period, the subject will be considered a non-responder for all diary time points up to and including the 2-hour diary time point for that treatment period.
5. No imputation will be done for the 24-hour time point (observed cases only).
6. Otherwise, missing diary data up to the 2-hour time point will be imputed by the last observation carried forward (LOCF).

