## **5. EFFICACY ANALYSES**

### **5.1. Primary Efficacy Endpoint in Part 1**

A patient diary is used to collect the patients' self-assessment of headache pain intensity. Pain intensity is rated on a 4-point scale: severe (3), moderate (2), mild (1), and none (0).

The primary efficacy endpoint is the proportion of subjects with pain-free status at the 2-hour time point for the high dose group during the double-blind phase of the study. Pain-free status is defined as a reduction in the headache pain intensity rating from moderate (2) or severe (3) pain at predose to none (0) at 2-hour post dose, without using rescue medication and without napping/sleeping prior to the 2-hour assessment.

For the primary efficacy endpoint analysis, all high-dose subjects in the FAS are included.

The primary endpoint will be analyzed using a generalized estimating equation (GEE). The model includes treatment, period, sequence, weight group (at randomization), and predose (immediately prior to study drug administration) headache pain intensity. The logit link function is used with an unstructured within subject covariance matrix. Odds ratio, p-value for the treatment effect and the corresponding 95% confidence interval will be presented.

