#### **5.2.1.6. Repeated Measures Analysis**

The primary endpoint will also be analyzed using a generalized estimating equation (GEE) using results from all post-dose timepoints (0.5, 1, 2 and 24 hours). The model will include treatment, period, sequence, weight group (at randomization), predose (immediately prior to study drug administration) headache pain intensity, timepoint as time factor and treatment by timepoint interaction. The logit link function will be used with an unstructured within subject covariance matrix. Odds ratio, p-value for the treatment effect and the corresponding 95% confidence interval will be presented for each timepoint. If the model fails to converge due to the unstructured covariance matrix, a simpler covariance matrix will be employed in the order of 1) autoregressive (1) [SAS PROC GEE type = AR(1)], 2) exchangeable [type = EXCH]. The first covariance structure that does not have a convergence problem will be the one used for the analysis.

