### **5.3. Secondary Efficacy Endpoints in Part 1**

Secondary efficacy endpoints include the following:

- Proportion of subjects with pain-free status 2-hour postdose for low dose group
- Proportion of subjects with pain-free status at 30 minutes, 1-hour, and 24-hour postdose (will also be performed for the subgroups defined in section 2.4 for the high dose group)
- Proportion of subjects without photophobia at 30 minutes, 1-hour, 2-hour, and 24-hour postdose
- Proportion of subjects without phonophobia at 30 minutes, 1-hour, 2-hour, and 24-hour postdose
- Proportion of subjects without nausea at 30 minutes, 1-hour, 2-hour, and 24-hour postdose
- Proportion of subjects with a headache response (defined as a reduction in headache severity from moderate (2) or severe (3) to mild (1) or none (0)) at 30 minutes, 1-hour, 2-hour, and 24-hour postdose (will also be performed for the subgroups defined in section 2.4 for the high dose group)

- Proportion of subjects who use rescue medication within 2, 3, 4 and up to 24 hours postdose. Note: if subject diary includes records of rescue medication that started prior to the start of migraine, such medications will be ignored as incorrect diary entry. If rescue medications are recorded with missing start date/time, worse case will be assumed, i.e. that the rescue medication was taken at the same time as the migraine started.
- Proportion of subjects with headache recurrence during 2 to 24 hours postdose for the subset of subjects who attained a 2-hour pain-free response
- Proportion of subjects with headache recurrence (with headache severity higher than that at 2 hours) during 2 to 24 hours postdose for the subset of subjects who attained a 2-hour headache response
- Proportion of subjects with sustained headache response 2 to 24 hours postdose defined as the proportion of subjects who attained a 2-hour headache response and who did not experience a headache recurrence (pain intensity moderate or severe) between 2 and 24 hours
- Proportion of subjects with sustained pain free response 2 to 24 hours postdose defined as the proportion of subjects who attained a 2-hour pain free response and who remained pain free between 2 and 24 hours

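### Rescue medication stops counting as failure at 2 hours, so a rescued attack can be scored as a 24-hour response

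*SAP*

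**What the plan says.** **Handling of rescue.** SAP section 2.5.1.1, rule 3, covers rescue taken within 2 hours of dosing. Such a subject is a non-responder "for all the subsequent diary time points after rescue for that treatment period up to and including the 2-hour time point". Rule 5 then says "No imputation will be done for the 24-hour time point (observed cases only").

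**When rescue is allowed.** Under section 1.1, a child without satisfactory relief by 2 hours may take the permitted pre-study medication "at that time or at any time thereafter, if the headache does not resolve or if it recurs". Triptans and ergots are excluded for 24 hours.

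**Endpoint definitions.** The primary definition in section 5.1 requires pain-free status "without using rescue medication and without napping/sleeping prior to the 2-hour assessment". Section 5.3 lists "Proportion of subjects with pain-free status at 30 minutes, 1-hour, and 24-hour postdose" with no rescue condition. Headache response, also assessed at 24 hours, is defined by severity alone. Sustained pain-free covers subjects "who attained a 2-hour pain free response and who remained pain free between 2 and 24 hours". Sustained headache response requires a 2-hour response without a later return to moderate or severe pain. Neither sustained definition mentions rescue.

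**Use of the data.** Section 5.3 gives every proportion endpoint a GEE model in each dose group. Section 5.2.1.6 puts the 0.5, 1, 2 and 24-hour results into one GEE. Section 5.3 also analyses rescue use within 2, 3, 4 and 24 hours, and time to rescue, as endpoints of their own.

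**The concern.** Up to 2 hours the plan is strict about rescue: it is a failure, and a missing start time is resolved as the worst case. After 2 hours, when section 1.1 first permits rescue, the rule lapses. A single attack can then be a failure at 2 hours and a success at 24 hours, with a rescue drug taken in between.

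Three results are affected. The 24-hour pain-free and headache response rates no longer describe response to the study treatment alone. The repeated-measures model compares treatments across time points at which response means different things. The sustained endpoints, whose name implies a lasting response to study treatment, have no rule that uses rescue as evidence of failure. These comparisons are tested at 5% without multiplicity adjustment (section 2). The 24-hour pain-free and headache response analyses are repeated in the high-dose subgroups.

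**Working it through.** The plan states no figure on this point, so there is none to reproduce. The first check follows attacks through the rules; the second is an illustration on assumed rates.

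**1. Attacks scored as the plan is written**

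- *Moderate pain at 2 h, rescue at 3 h, no pain at 24 h.* Rule 3 does not apply, because rescue came after 2 h. Rule 5 takes the rating as recorded. Result: failure at 2 h, pain-free and headache responder at 24 h.
- *Rescue at 1 h, no pain at 24 h.* Rule 3 gives non-response after rescue up to 2 h and goes no further. Result: failure at 2 h, responder at 24 h.
- *Pain-free at 2 h, headache returns at 8 h, rescue, no pain at 24 h.* If the return is recorded and used, the attack fails the sustained wording. But section 1.1 schedules no rating between 2 and 24 h. Table 4 assigns everything from 151 to 2160 minutes to the 24-hour window, and section 2.9.2 then selects the record closest to the nominal time. An extra rating at 8 h would give way to one at 24 h. No rule reads rescue as failure, so the attack can be counted as sustained.

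**2. Size for the 24-hour endpoints**

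Let *a* be the proportion clear at 24 h without having taken rescue, *r* the proportion rescued, and *s* the share of rescued attacks clear at 24 h. Assume every attack has a 24-hour rating.

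- Rate under the plan: a + r × s
- Rate with rescue as failure: a
- Gap within a treatment: r × s
- Shift in the ZNS-placebo difference, with the same *s* in both: s × (r_ZNS − r_placebo)

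Assumed, not from the SAP: r = 40-50% on placebo, 30-35% on ZNS; s = 60-80%.

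Gap on placebo: 0.40 × 0.60 = 24 points to 0.50 × 0.80 = 40 points. Gap on ZNS: 0.30 × 0.60 = 18 points to 0.35 × 0.80 = 28 points.

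Shift in the difference, in percentage points:

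| Rescue, placebo | Rescue, ZNS | s = 60% | s = 80% |
|---|---|---|---|
| 40% | 35% | -3 | -4 |
| 40% | 30% | -6 | -8 |
| 50% | 35% | -9 | -12 |
| 50% | 30% | -12 | -16 |

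The full range is -3 to -16 points.

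**3. A second set of assumptions**

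Suppose rescue is equally likely in both treatments among attacks not otherwise clear. Let *p* be the rescue-free 24-hour rate (assumed 25% on placebo and 36% on ZNS, a gap equal to the 0.11 in section 1.2), and let *r* now be the share of the remaining attacks that are rescued.

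- Apparent rate: p + (1 − p) × r × s
- Apparent difference: 0.11 × (1 − r × s)
- r = 0.3, s = 0.5: 0.11 × 0.85 = 0.094 (36% v 46%)
- r = 0.7, s = 0.9: 0.11 × 0.37 = 0.041 (72% v 76%)

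The shift is about -1.6 to -6.9 points. The direction is the same, because fewer placebo attacks are clear without rescue and so more of them are open to rescue.

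**The case against.** Using the 24-hour rating whatever rescue was taken is a recognised strategy. Rule 5 is explicit, and rescue use is reported separately to 24 hours. This stands in part: such an analysis is legitimate if chosen and labelled. But the SAP gives no reason for changing the treatment of rescue after 2 hours, and its own repeated-measures model combines both definitions.

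It could also be said that the rescue-free clause in section 5.1 carries over to 24-hour pain-free. The text ties that clause to the 2-hour assessment, and headache response has no such clause to carry over.

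Four stronger readings are tempting but not supported:

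- *A child whose headache returned and was rescued meets the sustained definition.* A known recurrence fails the wording of section 5.3. The gap is in detection. The diary form and protocol are not shown, so whether recurrence is recorded separately cannot be settled here.
- *The shift measures what the rescue drug did.* Some rescued attacks would have been clear by 24 hours anyway; the categories in section 4.3 for typical untreated attacks run from under 3 to over 8 hours. The figures are the gap between two definitions.
- *Placebo attacks are known to be rescued more often.* This is plausible, but the SAP gives no rescue rates.
- *Every rescue should be counted as a recurrence.* That would conflict with the section 5.3 recurrence endpoint that requires severity above the 2-hour level: a child with unchanged mild pain who took rescue would become a recurrence.

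**Conclusion.** The point holds for 24-hour pain-free, 24-hour headache response and the 24-hour row of the repeated-measures GEE. Followed exactly, the plan credits rescued 2-hour failures as 24-hour successes.

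The direction and size rest on assumptions. If placebo attacks are rescued more often and the share then clear is the same in both treatments, the difference is pulled towards zero. The assumed rates give -3 to -16 points, and the equal-propensity illustration gives about -1.6 to -6.9. If the share clear differed between treatments, the shift could fall outside these ranges.

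For the sustained endpoints the point is narrower: a rescued recurrence that leaves no trace in the selected 24-hour record can count as sustained. How often that would happen cannot be judged from the SAP.

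A reader might infer that the main result is in doubt. It is not: rescue before the 2-hour assessment is already a failure for the primary endpoint. This is a clear gap in secondary and supportive analyses that should be closed before Part 1 is unblinded.

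**What to change.** - In sections 2.5.1.1 and 5.3, state that rescue medication taken after dosing and up to 24 hours postdose, or up to the 24-hour rating if that is earlier, makes the attack a non-response for 24-hour pain-free, 24-hour headache response, sustained pain-free and sustained headache response. The cutoff has to be fixed in this way because the Table 4 window runs to 2160 minutes (36 hours), whereas the rescue endpoints stop at 24 hours.
- State that this also applies when the 24-hour rating is missing, so that a rescued attack is not dropped as unobserved under rule 5.
- Apply the same rule to the 24-hour row of the GEE in section 5.2.1.6.
- Keep the observed 24-hour rate, whatever rescue was taken, as a labelled supportive line.
- Leave the recurrence endpoints on their pain-severity definitions.

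The cost is SAP wording and one derived flag, built from rescue times that the plan already uses for the rescue endpoints. No new data are needed. The downside is lower absolute 24-hour rates in both treatments.

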- Time to rescue medication. For those subjects who did not use rescue medication, the time to rescue medication is censored at 24 hours after dosing. Additionally, descriptive summary of time to rescue medication will be presented for those subjects who did take a rescue medication. Note: if subject diary includes records of rescue medication that started prior to the start of migraine, such medications will be ignored as incorrect diary entry. If rescue medications are recorded with missing start date/time, time to rescue medication will be imputed as zero.

For all proportion endpoints, a GEE model similar to the primary analysis will be conducted for the low dose group and high dose group separately.

For the time to use of rescue medication, a Cox proportional hazards model for crossover data ([France et al 1991](#)) with treatment, period, weight, and baseline headache pain intensity will be used.

Time to use of rescue medication will also be presented graphically using the Kaplan-Meier estimates.

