### 6.4. Prior, Concomitant, and Rescue Medications

Prior and concomitant medications will be coded using the current version of World Health Organization (WHO) Drug Dictionary.

Prior medications are defined as medications taken and stopped prior to the first dosing date of study drug (placebo run-in). Concomitant medications for Part 1 are defined as medications taken while a subject took study drug in Part 1 or prior to taking study drug and continued during Part 1, up to Visit 4 date. Concomitant medications for Part 2 are defined as medications taken at any time on or after the date of Visit 4. Use of concomitant medications will be summarized by ATC Level 2 class, preferred name, study period, and within the Double-Blind period by treatment, using the number and percentage of subjects in the safety analysis set for Part 1 and in the OLE analysis set for Part 2. A subject reporting the same medication more than once in the same period will be counted only once when calculating the number and percentage of subjects

who received that medication. The summary will be ordered alphabetically by medication class (WHODrug ATC 2 Term) and preferred term (WHODrug Product term).

No formal statistical testing is planned for prior and concomitant medications.

Rescue medications are defined as those used after the study drug treatment for further alleviation of pain associated with the migraine attack, and is recorded on the subject's diary. Note: if subject diary includes records of rescue medication that started prior to the start of migraine, such medications will be ignored as incorrect diary entry. The use of rescue medication in Part 1 will be summarized by ATC Level 2 class, preferred name and treatment using the number and percentages of subjects in the safety analysis set. A subject reporting the same medication more than once will be counted only once when calculating the number and percentage of subjects who received that medication. The summary will be ordered alphabetically by medication class (WHODrug ATC 2 term) and preferred term (WHODrug Product term). The time to the use of rescue medication will also be summarized. Details are provided in Section 5.3.

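### Undated rescue is timed at migraine start, normally before dosing, so read literally the worst-case rule misses the postdose windows of headache response and rescue use and conflicts with the zero used for time to rescue

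*SAP*

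**What the plan says.** Section 2.5.1.1 rule 3 has three parts that matter here.

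- Its trigger is timed from dosing: "If a subject receives rescue medication within 2 hours after dosing with study drug for a particular treatment period".
- Its consequence runs forward from the rescue: "the subject will be considered a non-responder for all the subsequent diary time points after rescue", up to and including 2 hours.
- Its note covers bad or missing times. Entries that predate the migraine are dropped ("records of rescue medication that started prior to the start of migraine, such medications will be ignored as incorrect diary entry"). For entries with no start date or time, "worse case will be assumed, i.e. that the rescue medication was taken at the same time as the migraine started".

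Section 5.3 repeats the migraine-start note inside the endpoint "Proportion of subjects who use rescue medication within 2, 3, 4 and up to 24 hours postdose". For the time-to-rescue endpoint in the same section the rule differs: "If rescue medications are recorded with missing start date/time, time to rescue medication will be imputed as zero". Children without rescue are censored there at 24 hours after dosing, so zero on that scale is the dosing time.

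Section 6.4 adds a general definition: "Rescue medications are defined as those used after the study drug treatment for further alleviation of pain".

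Section 5.1 defines the primary endpoint, pain-free status at 2 hours, with its own condition that no rescue was used before the 2-hour assessment. The headache response definition in section 5.3 has no such condition.

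**The concern.** The note is meant to be conservative: when the time of rescue is unknown, assume the time least favourable to the child's response. The anchor chosen does not achieve this as worded. Children dose after the pain has become moderate or severe, so migraine start normally lies before dosing, while the rule and the endpoints it serves count time from dosing onward. A time placed before dosing falls outside those windows.

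Two things are at stake. Endpoints that depend on rule 3 alone to deal with rescue could credit a response to a child who took rescue at an unknown time. And a single diary record could be handled in opposite ways by two rescue endpoints in the same section.

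**Working it through.** No figure in the SAP is at issue, so the check is one of timing. Put dosing at t = 0 minutes and let L be the time from migraine start to dosing. The imputed rescue time under section 2.5.1.1 and the rescue-use bullet of section 5.3 is t = −L.

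**Values of L.** Section 1.1 has the child dose within about 20 minutes of the pain reaching moderate or severe intensity. Table 4 in section 2.9.2 places that moment between −60 and 0 minutes from dosing. Migraine start cannot be later than that moment, so L is at least 0 and usually positive. I used L = 0, 1, 20 and 60; the value 1 shows that any positive lag is enough.

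**Conditions tested.**
- Rule 3, read inclusively: 0 ≤ t ≤ 120.
- Rescue-use windows: 0 ≤ t ≤ 120, 180, 240 or 1440.
- Section 5.1 exclusion from 2-hour pain-free status: t < 120, with no lower limit.
- Time to rescue: fixed at 0 whatever L is.

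| L (min) | imputed t | rule 3 met | in any rescue-use window | barred from 2-hour pain-free by 5.1 | time in Cox model |
|---|---|---|---|---|---|
| 0 | 0 | yes, if 0 is included | yes, if 0 is included | yes | 0 |
| 1 | −1 | no | no | yes | 0 |
| 20 | −20 | no | no | yes | 0 |
| 60 | −60 | no | no | yes | 0 |

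The record is not discarded: only entries earlier than migraine start are ignored, and this one is placed exactly at migraine start. It stays in the data with a time that triggers nothing.

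**Consequences by endpoint, on the literal reading with L > 0.**
- Pain-free at 2 hours (primary): the child is a non-responder through section 5.1, whatever rule 3 does.
- Headache response at 0.5, 1 and 2 hours: only rule 3 removes rescued children, and it is not triggered. A child who goes from severe to mild at 2 hours stays a responder.
- Sustained headache response, and recurrence among 2-hour headache responders: both inherit that 2-hour status.
- Pain-free at 30 minutes and 1 hour, which also enter the repeated-measures analysis of section 5.2.1.6: unclear, because the section 5.1 condition is written for the 2-hour assessment.
- Rescue use within 2, 3, 4 and 24 hours: the child counts as not rescued.
- Time to rescue: the same child is an event at time 0.

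The 24-hour pain and headache-response assessments are outside rule 3, which stops at 2 hours.

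**After moving the anchor to dosing.** With t = 0 and an inclusive bound, rule 3 is met. The child is a non-responder at 0.5, 1 and 2 hours, is a rescue user in all four windows, and agrees with the Cox model. The primary classification is the same before and after.

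**The case against.** The strongest reply is that the intent is plain. The sentence sits inside rule 3, calls itself the worst case, and makes sense only as a way of applying that rule. If rescue is placed at migraine start, every postdose diary point up to 2 hours follows it. A programmer would have to impute an unfavourable time and then use it to exempt the child. The same holds for the rescue-use bullet, where the note is part of the endpoint and is most naturally read as making the child a rescue user. Table 4 also allows L = 0, so a negative time is usual but not universal.

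Most of this stands, and it makes the defect a risk in implementation, not a certain error. It does not remove it: the stated rule does not carry out the stated intent, and the zero for time to rescue shows that the SAP itself uses two anchors for one record.

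A reader might go further and infer that the child stays pain-free on the primary endpoint, so that each such child moves a treatment's rate by 1/240 = 0.42 percentage points in the high-dose group. Section 5.1 does not support this. Its condition has an upper limit at the 2-hour assessment and no lower limit at dosing, so rescue placed at migraine start already excludes the child.

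A reader might also argue from section 6.4 that a predose time stops the entry being rescue at all, which would reopen the primary endpoint. That is too strong. An undated diary entry is already recorded as rescue, and section 6.4 itself discards only entries earlier than migraine start.

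**Conclusion.** The point holds as an inconsistent time anchor with consequences for secondary endpoints. Whenever migraine start precedes dosing, the imputed time literally satisfies neither rule 3 nor any postdose rescue window, and it disagrees with the zero used for time to rescue. The exposed endpoints are headache response at 0.5, 1 and 2 hours, the sustained-response and recurrence endpoints built on 2-hour headache response, and the rescue-use proportions. Pain-free status at 30 minutes and 1 hour is ambiguous. The primary endpoint is not affected.

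No size can be given. The SAP does not state how often rescue is recorded without a start time, and only children with a qualifying reduction in pain would change on headache response. The conclusion rests on reading the windows literally; a programmer who follows the evident intent would reach the conservative result.

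**What to change.** In section 2.5.1.1 rule 3 and in the rescue-use bullet of section 5.3, replace migraine start with the time of study drug dosing as the imputed time for undated rescue, and say that time 0 is included. This matches the time-to-rescue rule.

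Moving the anchor alone is not quite enough, because a strict reading of a postdose window could still exclude time 0. So also state the outcome directly: such children are non-responders at 0.5, 1 and 2 hours for that treatment period and count as rescue users in every postdose window.

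The cost is a wording change in two places, made before unblinding. It needs no new data and leaves the primary analysis unchanged.

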### **5.5. Changes From Protocol-Specified Efficacy Analyses**

If a subject naps or sleeps within 2 hours after dosing with study drug for a particular treatment period, the subject will be considered a non-responder for all diary time points up to and including the 2-hour diary time point for that treatment period.

The randomized population is replaced by the full analysis set. The completers population is further clarified as the double-blind completers analysis set.

The protocol inadvertently states that the McNemar's test was to be performed for Period 1 data. This SAP has corrected that the McNemar's test will be performed for each sequence.

Additional endpoints were added to the OLE endpoints to further elucidate the effect of ZNS:

- Proportion of subjects experiencing 2-hour pain free for  $\geq 20\%$ , 40%, 60%, and 80% of their treated moderate to severe migraine headaches.
- Proportion of treated moderate to severe migraine headaches that reduce to pain free at 2 hours:
  - o Descriptive summaries (mean, SD, median, min, max)
  - o Categorical summaries of  $\geq 20\%$ , 40%, 60%, and 80% of treated headaches

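### Rule 4 fails 30-minute and 1-hour ratings recorded before a nap, although the matching rescue rule fails only later time points

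*SAP*

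**What the plan says.** Section 2.5.1.1 of the SAP lists six rules for the headache diary. Two of them deal with events in the first 2 hours after dosing.

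- **Rule 3 (rescue).** A child who takes rescue medication within 2 hours is "considered a non-responder for all the subsequent diary time points after rescue", up to and including 2 hours. Ratings before the rescue stand.
- **Rule 4 (nap or sleep).** A child who naps or sleeps within 2 hours is "considered a non-responder for all diary time points up to and including the 2-hour diary time point". The rule does not refer to when the nap began.

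Section 5.5 lists rule 4 among the changes from the protocol, in the same words ("If a subject naps or sleeps within 2 hours after dosing with study drug for a particular treatment period", and so on), and gives no reason for its reach.

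Section 5.1 defines the primary endpoint, 2-hour pain-free status, as achieved "without using rescue medication and without napping/sleeping prior to the 2-hour assessment". Section 5.3 makes the earlier time points secondary endpoints: "Proportion of subjects with pain-free status at 30 minutes, 1-hour, and 24-hour postdose", and headache response at 30 minutes, 1 hour, 2 hours and 24 hours. Each is analysed by GEE separately for high and low dose, and by subgroup for high dose. Section 5.2.1.6 enters the 0.5-, 1-, 2- and 24-hour results in a repeated-measures GEE and reports an odds ratio for each time point.

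**The concern.** A nap at 90 minutes cannot have affected a rating given awake at 30 or 60 minutes. Rule 4 nevertheless replaces that rating with a failure. Section 2.5.1 presents these rules as handling missing diary data, but here the rating is present and is overwritten because of something that happened later.

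As a result, the 30-minute and 1-hour endpoints no longer measure what section 5.3 names. Each becomes a composite: relief at that time and no nap at any point up to 2 hours. A reader of the early-time-point tables would take them as showing how soon relief begins, and would not see that observed successes had been removed. If napping differs between treatments, the comparison also carries a difference in later sleep.

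**Working it through.** **1. The two rules applied to one child.** The child rates pain as none at 30 minutes and at 1 hour, and the event occurs at 90 minutes.

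| Event at 90 minutes | 30 min | 1 h | 2 h |
|---|---|---|---|
| Rescue (rule 3) | pain-free, kept | pain-free, kept | failure |
| Nap (rule 4 as written) | failure | failure | failure |
| Nap (rule 4 limited to later ratings) | pain-free, kept | pain-free, kept | failure |

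The 2-hour result is the same in all three rows. The 24-hour result lies outside rule 4, and rule 5 leaves it as observed.

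**2. Size.** The SAP states no figure to reproduce: it gives neither nap rates nor expected 1-hour rates. All inputs here are assumptions. Let p be the true 1-hour response rate in an arm. Let q be the share of those responders who first nap after the 1-hour rating but within 2 hours. Under rule 4 the analysed rate is p(1 − q).

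*Headache response, 45% on ZNS v 30% on placebo.* The true difference is 15 points and the odds ratio is (0.45/0.55)/(0.30/0.70) = 1.91.

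| q ZNS | q placebo | ZNS | Placebo | Difference (points) | Odds ratio |
|---|---|---|---|---|---|
| 10% | 10% | 0.45 × 0.90 = 40.5% | 0.30 × 0.90 = 27.0% | 13.5 | 1.84 |
| 20% | 20% | 0.45 × 0.80 = 36.0% | 0.30 × 0.80 = 24.0% | 12.0 | 1.78 |
| 30% | 30% | 0.45 × 0.70 = 31.5% | 0.30 × 0.70 = 21.0% | 10.5 | 1.73 |
| 30% | 20% | 31.5% | 24.0% | 7.5 | (0.315/0.685)/(0.24/0.76) = 1.46 |
| 20% | 30% | 36.0% | 21.0% | 15.0 | (0.36/0.64)/(0.21/0.79) = 2.12 |

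*Pain-free, 20% v 10%, in the planned 240 high-dose children.* The true difference is 10 points, odds ratio 2.25.

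- Equal q of 10% to 30% recodes 240 × 0.20 × q = 4.8 to 14.4 observed successes on ZNS and 240 × 0.10 × q = 2.4 to 7.2 on placebo. The difference falls to 9-7 points and the odds ratio to 2.22-2.16.
- q of 30% on ZNS v 10% on placebo gives 14% v 9%: 5 points, odds ratio 1.65.
- q of 10% v 30% gives 18% v 7%: 11 points, odds ratio 2.92.

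So equal napping shrinks the effect, modestly on the odds-ratio scale that the SAP reports. Unequal napping can shrink or enlarge it.

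**The case against.** **The rule is prespecified, declared in 5.5 and applied alike to both treatments.** True, and the SAP nowhere says that naps and rescue must be handled the same way. But 5.5 gives no reason for reaching back. Applying the rule alike does not restore the lost successes, and it does not protect the comparison if napping differs by treatment.

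**Rules 1 and 2 also fail all three time points.** They do so when the predose rating is missing or when every postdose rating to 2 hours is missing, so no evaluable success is discarded. Rule 4 discards evaluable ratings.

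**Few children are affected.** This stands in part. The 1-hour result changes only for responders who first nap after that rating and before 2 hours; earlier nappers fail at 1 hour under either wording.

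**The nap start time may not be recorded.** This stands. Rule 3 provides for missing rescue times, whereas rule 4 says nothing about timing, which would fit a yes/no diary item. The SAP does not settle it, so the fix must work in both cases.

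Three stronger readings are tempting but not supported:

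- *That rule 4 biases the primary result or contradicts 5.1.* Section 5.1 concerns the 2-hour outcome only and already excludes a nap before it.
- *That the rule always works against ZNS.* The direction depends on which arm naps more, and the SAP has no data on that.
- *That these endpoints are the only evidence on onset.* Section 5.3 also lists absence of photophobia, phonophobia and nausea at 30 minutes and 1 hour. The SAP does not say whether rule 4 extends to them.

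**Conclusion.** The point holds for the early secondary endpoints. Followed as written, rule 4 counts as failures some children who were observed to be pain-free, or to have responded, before they slept. This affects 30-minute and 1-hour pain-free status and headache response at both dose levels, the high-dose subgroup analyses of these, and the early time points of the repeated-measures GEE. The 2-hour primary endpoint, the recurrence and sustained-response endpoints that start from 2-hour status, and the 24-hour endpoints are not affected.

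The inconsistency with rule 3 rests on the text alone. Its size rests wholly on assumed response and nap rates. Under the 45% v 30% example, equal napping of 10% to 30% costs 1.5 to 4.5 of 15 points. With unequal napping the result ranges from half the true difference to an unchanged difference with an inflated odds ratio. The rule therefore cannot be defended as simply conservative. It should be changed, but it does not threaten the trial's main conclusion.

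**What to change.** In sections 2.5.1.1 (rule 4) and 5.5:

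1. Limit the failure to diary time points whose actual assessment time is after the start of the nap or sleep, up to and including 2 hours. Keep earlier observed ratings. Specify actual time because the 1-hour window in Table 4 runs from 46 to 90 minutes; where a rating is missing, use the nominal time.
2. State that the 2-hour time point still fails for any nap within 2 hours of dosing. Otherwise a 2-hour rating taken early in its 91-150 minute window, with a nap soon after, would change status. This keeps the primary endpoint exactly as it is.
3. Where the nap start time is missing, keep the current rule as the worst case, as rule 3 does for missing rescue times.
4. If the nap start time is not collected at all, keep the current rule and also report the 30-minute and 1-hour endpoints with observed ratings as a supplementary analysis.
5. Say whether rule 4 applies to the photophobia, phonophobia and nausea endpoints.

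The cost is SAP wording and one derivation rule. The drawback is reliance on a recorded nap start time, which items 3 and 4 cover.
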